improvement training packages that will be delivered to more than 350 healthcare providers in 60 healthcare facilities in this program, with an appropriate performance framework to follow-up key-indicators around ANC-PNC, with regard to HIV, TB and malaria in particular.

Overall, with 6,936 ANC visits (of which 3,248 attending for the first/booking visit) and 826 PNC visits in the month of the survey – giving an estimate of 93,144 women annually – there is a wide scope for reaching a substantial population of women and babies to provide them with both basic services and disease-specific care.

There was good availability of services reported for the three diseases; 90% facilities offered HIV screening and 78.3% also offered treatment; 91.7% healthcare facilities offered malaria screening and treatment; 35% offered TB screening and treatment. However, it was evidenced that despite the full availability of rapid diagnostic tests for HIV (100%), the systematic screening for HIV in ANC was incomplete: HIV tests were conducted for 2,501 women at ANC (1,791 among them at booking visit – 55% of all women coming for ANC1) and 237 (28.7%) at PNC. Besides, 15.5% of women were tested for syphilis at ANC1, and none at PNC, even though 60% of healthcare facilities had rapid diagnostic tests. Furthermore, there was no screening for TB in ANC or PNC (1 woman - ~0%), suggesting that there are missed opportunities for identifying positive cases linked to the clinical screening and the decision to test women. For malaria, 413 (12.5%) women were tested for malaria at ANC and 17 (2.1%) at PNC with all those testing positive starting treatment. The high positivity rate among women tested (47.5%), suggested that the low proportion of women tested in ANC and especially in PNC could result in missed opportunities to identify and treat women. Again, there was a reported good availability of malaria testing kits (80%), therefore ruling out lack of availability as a sole explanation for this. Regarding provision of intermittent preventive treatment of malaria in pregnancy (IPTp), 54% of eligible women received prophylaxis in ANC, despite Sulfadoxine-pyrimethamine (SP) being found in 94.3% of healthcare facilities. This is indicative of the opportunity to improve the provision of basic and disease specific care.

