3.4 Outcomes

This trial will have two primary outcomes, one around essential components for ANC, and one for essential components for PNC.

Outcome 1 (ANC): Essential components included in the composite measure of integrated services specific to ANC visits are listed below.

- EC1 = Respectful maternity care indicators:
 - Introductions, greeting the woman, consent, questions
- EC2 = Screening for Pre-eclampsia:
 - Measure BP

- Test urine for proteinuria
- EC3 = Screening for, prevention and management of Anaemia:
 - Measure Haemoglobin
 - Provide ferrous sulphate with folic acid
- EC4 = Screening for, prevention and management of Malaria:
 - Checked for clinical symptoms and test for Malaria if relevant
 - Provide treatment if needed
 - Provide bed nets if not provided yet
 - Provide Intermittent Presumptive treatment
- EC5 = Screening for, prevention and management of HIV:
 - Test for HIV
 - Provide Prevention of mother to child transmission care (PMTCT)
 - Provide anti-retroviral drugs (ARV) for mother if needed
- EC6 = Screening for, prevention and management of Syphilis:
 - Test for syphilis
 - Provide antibiotics if needed
- EC7 = Screening for, prevention and management of Tuberculosis (TB):
 - Checked for clinical symptoms and test for TB
 - First line TB drugs or referral if needed
- EC8 = Prevention of Tetanus in mother:
 - Tetanus toxoid vaccination
- EC9 = Screening and counselling for mental health and domestic violence:
 - Screening tools
 - Counselling services
- EC10 = Estimation of BMI:
 - Assess maternal height
 - Assess maternal weight
- EC11 = Prevention of post- and pre-term birth:
 - Estimate gestational age
- EC12 = Assessment of foetal wellbeing during pregnancy, Screening for multiple pregnancy, abnormal lie and presentation during pregnancy:
 - Assess growth using fundal height measurement
 - Assess foetal heart rate (FHR)
 - Abdominal palpation
- EC13 = Provide advice on birth preparedness and danger signs of pregnancy:
 - Consultation

The outcome for each ANC visit will be a score which measures the proportion of the above components that was delivered during that visit (EC_ANC).

The score will measure the proportion of essential components delivered in full. All thirteen essential components listed above are applicable for ANC. Some essential components

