involve multiple components, at least one of which is always applicable; some components are only applicable to a subset of clients, eg HCP counsels the woman about mental health is only applicable if the client's response to a previous question is cause for concern. All essential components will carry a weight of 1. The overall score will be derived by aggregating the weighted scores for each essential component which will then be converted to a percentage. Six essential components are binary; hence the score can only be 0 (not achieved), or 1 (achieved and single weighted); in some cases the determination of this involves an algorithm. The other seven essential components are not binary as they have sub-components assessed independently and thus may be partially achieved and carry an intermediate score, eg a multiple of 0.25 for essential component 1 (respectful maternal care).

Outcome 2: Essential components included in the composite measure of integrated services specific to PNC visits are listed below.

- EC1b = Respectful maternity care indicators:
 - Introductions, greeting the woman, consent, questions
- EC2b = Screening for Pre-eclampsia:
 - Measure BP
- EC3b = Screening for, prevention and management of Anaemia:
 - Measure Haemoglobin
 - Provide ferrous sulphate with folic acid
- EC4b = Screening for, prevention and management of Malaria:
 - Checked for clinical symptoms and test for Malaria if relevant
 - Provide bed nets if not provided yet
- EC5b = Screening for, prevention and management of HIV:
 - Test for HIV
 - Provide Prevention of mother to child transmission care (PMTCT)
 - Provide anti-retroviral drugs (ARV) for mother and baby
- EC6b = Screening for, prevention and management of Syphilis:
 - Test for syphilis
 - Provide antibiotics if needed
- EC7b = Screening for, prevention and management of Tuberculosis (TB):
 - Checked for clinical symptoms and test for TB
 - First line TB drugs or referral if needed
- EC8b = Prevention of Tetanus in mother and baby:
 - Tetanus toxoid vaccination
- EC9b = Screening and counselling for mental health and domestic violence:
 - Screening tools
 - Counselling services
- EC10b = Provide advice and support regarding breastfeeding:
 - Consultation

- EC11b = Offer postpartum contraception:
 - Consultation
- EC12b = Monitor newborn growth:
 - Weigh the baby
- EC13b = Clinical examination of the mother:
 - Examine the mother
- EC14b = Clinical examination of the baby:
 - Examine the baby

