Appendix 2: Tools for data collection for observation

Below is the observation checklist. Essential components are numbered slightly differently than appendix 1 for the construction of the score. The scoring attributes will not appear for the data collectors and only be used by the statistician at time of analysis. Each essential component is score 1, for a total of 13 essential components for ANC visits, and 16 for PNC visits. Essential components can be a sum of x number of subcomponents as indicated in the table. Each subcomponent needs all applicable questions to be observed (Please see examples of algorithms at the end of appendix).

Please note this tool is to be deployed on an electronic platform, therefore the formatting of the tool will be visually different to what is included here. All boxes starting with "If" will only appear depending on the answer to the relevant condition (e.g. treatment will only be asked for women tested positive). The "Not applicable" answer is available for questions which depend on the gestational age and type of visit. The tool will be deployed in FRENCH.

OBSERVATION

Variable label	Answers	Conditionality	Scoring
GENERAL			
Please select the region	[dropdown menu]		
Please select the name of the facility	[dropdown menu]		
If 'Other' facility, please specify	[free text]		
Date of survey	[select from calendar]		
Name of person completing form	[free text]		
Anonymous ID of HCP	[free text]		
ANC			
ANC general information			
First/subsequent contact	0 - Subsequent contact, 1 - first contact -99 INF		
Which subsequent visit was it?	2- ANC2, 3- ANC3, 4- ANC4, 5- ANC5, 6-ANC6, 7- ANC7, 7-ANC8	Only to appear if previous answer = 0 – Subsequent visit	
Gestational age (weeks)	[integer]		
Who gave information about gestational age	1 - Woman, 2 - Healthcare provider, 3 - Other (specify)		
If other, specify	[free text]		
Women arrival time in the facility	[time]		
Comments	[free text]		

ANC contact		
EC1: Respectful maternity		1 (sum of all
care		subcomponents)
RMC subcomponent 1		0.25 (Points given if all applicable questions are observed)
The healthcare provider		
(HCP) introduced		
themselves to the		
pregnant woman	0 - No, 1 - Yes	
The HCP greeted the		
pregnant woman (or		
answered if woman		
greeted first)	0 - No, 1 – Yes	
RMC subcomponent 2		 0.25
The HCP asked the		
pregnant woman to take a	0 - No, 1 - Yes, -88 - Not	
seat	applicable (no chairs)	
The HCP asked the		
pregnant woman if she		
came with a companion		

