(or the woman already		
declared it herself)	0 - No, 1 – Yes	
If the woman had a		
companion with her, was		
the companion allowed to		
be with the pregnant		
woman during ANC	0 - No, 1 - Yes, -88 - Not	
consultation?	applicable (no companion)	
RMC subcomponent 3		0.25
The HCP asked how the		
pregnant woman was and		
asked about any problems	0 - No, 1 - Yes,	
RMC subcomponent 4		0.25
The HCP explained to the		
woman what they would		
like to do, prior to all		
examination or		
investigation	0 - No, 1 - Yes,	
The HCP explained that the		
findings of any		
examination and/or		
investigation would be	0 - No, 1 - Yes, -88 - Not	
confidential	applicable (no testing)	
The HCP explained the		
findings of investigations		
or examinations to the		
woman	0 - No, 1 – Yes	

EC2 = Screening for,			1
prevention and			
management of Anaemia			
Anaemia subcomponent 1			0.5
Blood taken to test	0 - No, 1 - Yes		
haemoglobin level	•		
If yes, HCP recognised and	0 - No, 1 – Yes, -88 Not		
acted upon abnormal	applicable		
findings			
Anaemia subcomponent 2			0.25
Iron tablets and folic acid	0 - No, 1 - Yes		
were given or prescribed			
for the pregnant woman			
Anaemia subcomponent 3			0.25
HCP counselled the	0 - No, 1 - Yes		
woman about dietary			
sources of iron			
Anaemia: Not in scoring			
If the woman was referred,			
what was the reason?	comment		
EC3 = Screening for Pre-			1
eclampsia			
Preeclampsia			0.5
Subcomponent 1			
The pregnant woman had			
her BP measured and			
noted in booklet	0 - No, 1 - Yes	0.1.	
If BP over 140/90 mmHg,		Only to	
HCP recognised and acted		appear if	
upon abnormal findings		answer to	
	0 - No, 1 – Yes, -88 – Not	previous question = 1-	
	applicable (BP normal)	Yes	
Preeclampsia	applicable (Br Hormal)	163	0.5
Subcomponent 2			0.5
The HCP checked urine for			
protein and noted in			
booklet	0 - No, 1 - Yes		
If yes, HCP recognised and	, , , , , , , , , , , , , , , , , , ,	Only to	
acted upon abnormal		appear if	
findings		answer to	
		previous	
		question = 1-	
	0 - No, 1 - Yes	Yes	
Preeclampsia: Not in			
scoring			
If the woman was referred,			
what was the reason?	comment		

EC4 = Screening for,			1
prevention and			
management of Malaria			
Malaria Subcomponent 1			0.5
HCP gave her the SP		Only to	
		appear if after	
	0 - No, 1 - Yes	1 st trimester	
HCP explained why it was		Only to	
important taking the SP		appear if	
		answer to	
		previous	
		question = 1-	
	0 - No, 1 - Yes	Yes	
HCP asked the woman			
whether she has			

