If ANC1 or no status indicated in booklet, syphilis testing was performed Did the woman test positive to syphilis? If test positive, antibiotic treatment was given (or prescribed if not available in facility) and noted in booklet If the woman was referred, what was the reason? EC7 = Screening for, prevention and management of Tuberculosis TB subcomponent 1	0 - No, 1 - Yes, -88 - Not applicable (Status indicated in booklet already) 0 - No, 1 - Yes 0 - No, 1 - Yes, -88 - Not applicable (Test negative)	appear if test performed Only to appear if test	

1 1100 1 11 15	I	I	1
HCP ask the woman if she			
was coughing	0 - No, 1 - Yes		
If the woman has a cough,	0 - No, 1 – Yes, -88 = Not		
HCP asks if it is productive	Applicable (no cough or		
	not asked)		
If the woman has a cough,	0 - No, 1 - Yes, -88 - Not		
HCP asks about duration of	Applicable (no cough or		
cough	not asked)		
TB subcomponent 3			0.4
HCP asked about night			
fever	0 - No, 1 - Yes		
Subsequent questions to			
subcomponent 2 or 3			
If productive cough, or		Only to	
night fever, TB testing was		appear if	
performed		productive	
perrormed		cough or	
	0 - No, 1 - Yes	night fever	
If tested, what kind of	1- Sputum 2- GenXpert 3-		
 	· '	Only to	
testing was performed?	Thorax radiography 4-	appear if	
	Other (please specify), -88	productive	
	- Not Applicable (test not	cough or	
	performed)	night fever	
If tested, did the woman		Only to	
test positive to TB?		appear if	
	0 - No, 1 - Yes, -88 - Not	productive	
	Applicable (test not	cough or	
	performed)	night fever	
If positive, the woman		Only to	
was offered treatment for		appear if	
HRZE quadritherapy TB		productive	
and noted in booklet	0 - No, 1 - Yes, -88 - Not	cough or	
	Applicable (test negative)	night fever	
TB: Not included in scoring	· · · · · · · · · · · · · · · · · · ·	· · · · · · · · · · · · · · · · · · ·	
If the woman was referred,			
what was the reason?	Comment		
EC8 = Prevention of	Comment		1
Tetanus in mother			1
HCP checked tetanus	0 No 4 Van		
vaccination status	0 - No, 1 - Yes		
If no status reported or		Only to	
vaccinal status not up to		appear if	
date, HCP provided	0 - No, 1 - Yes, -88 - Not	answer to	
tetanus vaccination	Applicable (5 injections for	previous = 1-	
	VAT already completed)	Yes	
If the woman was referred,			
what was the reason?	Comment		
EC9 = Screening and			1
counselling for mental			
health and domestic			
violence			

Mental subcomponent 1			0.5
HCP asked the woman			0.5
about her psychological			

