companion (or the woman			
already declared it herself)	0 - No, 1 – Yes		
If the woman had a	,		
companion with her, was	0 - No, 1 - Yes, -88 - Not		
the companion allowed to	applicable (no companion)		
	, , , , , , , , , , , , , , , , , , , ,	I	

be with the woman during ANC consultation?		
RMC subcomponent 3		0.25
The HCP asked how the		
woman was and asked		
about any problems	0 - No, 1 - Yes,	
RMC subcomponent 4		0.25
The HCP explained to the		
woman what they would		
like to do, prior to any		
examination and/or		
investigation	0 - No, 1 - Yes,	
The HCP explained that the		
findings of any testing	0 - No, 1 - Yes, -88 - Not	
would be confidential	applicable (no testing)	
The HCP explained the		
findings of all		
investigations or		
examinations to the		
woman	0 - No, 1 – Yes	
EC2b = Screening for,		1
prevention and		
management of Anaemia		
Anaemia subcomponent 1		0.5
Blood taken to test	0 - No, 1 - Yes	
haemoglobin level		
If yes, HCP recognised and	0 - No, 1 - Yes, -88 - Not	
acted upon abnormal	applicable (no abnormal	
findings	findings)	
Anaemia subcomponent 2		0.25
Iron tablets and folic acid	0 - No, 1 - Yes	
were prescribed for the		
woman		
Iron tablets and folic acid	0 - No, 1 - Yes	
were provided for the		
woman		
Anaemia subcomponent 3		0.25
HCP counselled the	0 - No, 1 - Yes	
woman about dietary		
sources of iron		
Anaemia: not in scoring		
If the woman was referred,		
what was the reason?	comment	
EC3b = Screening for		1
hypertension		
The woman had her BP		
measured and noted in	0 No 1 V	
booklet	0 - No, 1 - Yes	

If BP over 140/90, HCP	1	Only to	1
recognised and acted upon		appear if	
abnormal findings		answer to	
		previous	
	0 - No, 1 - Yes, -88 - Not	question = 1-	
	applicable (BP normal)	Yes	
EC4b = Screening for,			1
prevention and			
management of Malaria			
Malaria Subcomponent 1			0.5
HCP asked the woman			
whether she has			
Insecticide treated bed net	0 - No, 1 – Yes		
If no, HCP provided			
Insecticide treated bed net	0 - No, 1 – Yes		
Malaria Subcomponent 2			0.5
Temperature taken using			
a thermometer and			
recorded in booklet	0 - No, 1 – Yes		
Malaria testing was	O No 4 Voc		
performed	0 - No, 1 - Yes	Ordenta	
If test done, was the		Only to	
woman tested positive to	O No 1 Voc	appear if test	
malaria?	0 - No, 1 - Yes	performed	
If test was positive,		Only to	
antimalarials given to	0 - No, 1 – Yes, -88 – Not	appear if test performed	
the woman	applicable (Test negative)	'	
If test was negative and		Only to	

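### Appendix 2 scores two items, postnatal iron and TB treatment, more strictly than section 3.4 defines them

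*Protocol*

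**What the plan says.** Section 3.4 defines each visit's outcome as the proportion of essential components delivered, with 13 components for ANC and 16 for PNC, each of weight 1. The PNC score is to be built like the ANC score, with three components dropped and six added.

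For anaemia (EC3 and EC3b in section 3.4, EC2 and EC2b in the tool), the medication bullet is the same for both visit types: "Provide ferrous sulphate with folic acid". For tuberculosis (EC7 and EC7b) there are two bullets. The first covers checking symptoms and testing. The second reads "First line TB drugs or referral if needed".

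Appendix 2 turns these into points. Its introduction states: "Each subcomponent needs all applicable questions to be observed". A not-applicable "answer is available for questions which depend on the gestational age and type of visit".

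- **Iron, ANC tool.** One row, worth 0.25, asks whether tablets "were given or prescribed".
- **Iron, PNC tool.** Two rows share the 0.25. One asks whether tablets were prescribed, the other whether they "were provided for the" woman. Both are coded No or Yes only.
- **TB, ANC tool.** Testing and, after a positive test, the offer of HRZE are follow-up rows to subcomponent 2 or 3. Referral is a free-text comment under the label "TB: Not included in scoring".
- **TB, PNC tool.** The offer of HRZE appears if the mother's test is positive. There is no referral entry for the mother, while the row for the baby accepts referral.

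**The concern.** Both primary outcomes are sums of these points, so Appendix 2 is the operational definition of the endpoint. Where it is stricter than section 3.4, an act that the protocol defines as delivered care is recorded as not delivered.

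For iron, the same act by the same provider earns 0.25 at an ANC visit and nothing at a PNC visit. The stated differences between the two scores (components dropped and added) do not include a stricter iron criterion. Points then depend partly on whether a facility writes a prescription when it dispenses, which is not the professional practice the trial sets out to measure.

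For TB, a provider who screens, tests, finds a positive result and refers has done what section 3.4 lists. The tool gives that provider the same result on the affected subcomponent as one who did not screen.

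Timing matters. Appendix 2 says the scoring is applied at analysis, so the iron rule could still be repaired in the script. Maternal TB referral at PNC is not collected as an item, so no script could reliably recover it.

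**Working it through.** **Step 1. Reproduce the structure of the score.** Subcomponent weights in the ANC tool:

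- EC1: 4 × 0.25
- EC2: 0.5 + 0.25 + 0.25
- EC3, EC4, EC9 and EC13: 0.5 + 0.5 each
- EC7: 0.2 + 0.4 + 0.4
- EC5, EC6, EC8, EC10, EC11 and EC12: single components of weight 1

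This gives 13 components with total weight 13, six binary and seven with subcomponents, as section 3.4 states. For PNC, 13 − 3 + 6 = 16, which also agrees.

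**Step 2. Iron at PNC.** Take a visit where tablets are handed over and no separate prescription is written.

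| | Requirement | Result |
|---|---|---|
| Section 3.4 | provide the tablets | delivered |
| ANC tool | given or prescribed | 0.25 of 0.25 |
| PNC tool | prescribed = Yes and provided = Yes | 0 of 0.25 |

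The anaemia component can then reach at most 1 − 0.25 = 0.75. Loss on the visit score: 0.25/16 = 0.0156, or 1.56 percentage points. For scale:

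- Against the effect of 0.1 used in the section 3.6 simulations: 1.56/10 = 16% per affected visit.
- Against the detectable difference of 0.23 in Table 5: 1.56/23 = 6.8%.

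The documents do not say how often tablets are dispensed without a prescription. If the share of PNC visits is assumed to lie between 25% and 100%, the mean PNC score falls by 0.25 × 1.56 = 0.39 to 1.00 × 1.56 = 1.56 points.

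**Step 3. TB.** Take a woman who is asked every question, tested and found positive, then referred, with the HRZE row coded No.

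| | Requirement after a positive test | Result |
|---|---|---|
| Section 3.4 | first-line drugs or referral | delivered |
| ANC tool | offer of HRZE; referral unscored | row failed |
| PNC tool | offer of HRZE; no maternal referral entry | row failed |

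The follow-up rows carry no weight of their own and are attached to subcomponent 2 or 3 without a stated allocation. The failed row therefore removes 0.4 or 0.8, leaving the component at 0.6 or 0.2 (at PNC, assuming the baby row is met).

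- ANC: 0.4/13 = 3.08 points; 0.8/13 = 6.15 points.
- PNC: 0.4/16 = 2.50 points; 0.8/16 = 5.00 points.

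These are per affected visit. Each such visit per 100 lowers the mean ANC score by 3.08/100 = 0.03 to 6.15/100 = 0.06 points, and the mean PNC score by 2.50/100 = 0.025 to 5.00/100 = 0.05 points. The documents give no count of test-positive women who are referred. Section 2.1.3 reports TB screening of one woman in the survey month, so before training the number should be close to nil.

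**The case against.** **Provision and prescription are both good practice, so both may be required on purpose.** Nothing says so. Section 3.4 and Appendix 1 ask for provision, and the ANC tool accepts either route. The only scoring example announced in Appendix 2 concerns respectful maternity care, and no visible text overrides the rule for iron. However, a reader might infer that prescription alone should also earn the points at PNC under section 3.4. It does not support that: its word is provide. The clear conflict is limited to tablets provided without a separate prescription.

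**The TB tool agrees with section 3.4 on testing.** This stands. A reader might infer that a symptomatic woman referred without a test is also wrongly penalised. Because the 2018 survey reports that "35% offered TB screening and treatment", that reader might reckon 0.65 × 0.05 × 3.08 = 0.1 to 0.65 × 0.20 × 6.15 = 0.8 points on the mean ANC score, with an assumed 5% to 20% of women symptomatic. Section 3.4 offers referral as an alternative to drugs, not to the test, so failing the testing row is consistent with it and that range does not measure a contradiction. The survey also covered 60 facilities in twelve regions, whereas the trial is in N'Djamena only.

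**The PNC maternal antiretroviral rows look like the iron rows.** The parallel is weak. Prescribed or given, followed by provided, reduces in effect to provided, which matches EC5b. The HIV block also has no subcomponents, so the quoted rule does not govern it directly.

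**Dependence on stock is accepted.** Sections 3.2.3 and 3.7 plan to record availability for use in the analysis, and the paragraph on shortages before section 5 accepts their effect. That answers a complaint about stock. It does not explain failing an act that section 3.4 lists as delivery.

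**Conclusion.** The point holds for two items. The PNC iron rows contradict section 3.4 when tablets are provided without a separate prescription: 1.6 points on each such visit, and 0.39 to 1.56 points on the mean PNC score if 25% to 100% of visits are affected (assumed). The TB treatment row contradicts section 3.4 for a test-positive woman who is referred: 3.1 to 6.2 points on an ANC visit or 2.5 to 5.0 on a PNC visit, but few visits and a small effect on the mean. The TB figures assume that observers code a referral as no offer of HRZE.

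Two wider inferences go beyond the documents. The first is that such care scores zero outright: only the subcomponent does, anaemia can still reach 0.75 and TB 0.2 or 0.6, and referral of the baby is credited. The second is that the training effect is understated. The same rule applies before and after training, so the estimate moves only if the share of affected visits changes with training. That is possible, for example if training leads to more testing and so to more referrals, but it is not shown.

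This is a modest inconsistency in the definition of a primary outcome, worth correcting because correction before launch is cheap.

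**What to change.** Before launch, reconcile Appendix 2 with section 3.4:

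1. Score PNC iron and folic acid on one row, consistent with section 3.4 and the ANC tool. Since section 3.4 says provide and the ANC row also accepts a prescription, the sponsor should state once whether a prescription alone earns the points, and apply that to both visit types.
2. Add a structured Yes/No field for maternal TB referral in both tools, counting as the alternative to the treatment row only. Leave the testing row as it is unless section 3.4 is itself changed.
3. State whether the TB follow-up rows belong to subcomponent 2, subcomponent 3 or both.
4. Check the PNC antiretroviral rows for consistency with the ANC wording.

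The cost is a few edits to the electronic form and the scoring script. The separate prescribed and provided answers can be kept as descriptive data. These changes affect scoring, not care.
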